25.3.6 Analysis Methods

Primary Efficacy Endpoint

The primary efficacy endpoint is change from baseline in ABR for treated bleeds.

The primary analysis of the primary efficacy endpoint will be based on the 270-902 Rollover Subjects. The baseline ABR under FVIII prophylaxis will be based on the data collected in 270-902. The ABR post-BMN 270 infusion will be based the data collected in the efficacy evaluation period, defined as Week 5 to each subject's last visit up to the analysis data cutoff date.

Change from baseline in ABR will first be tested for non-inferiority with a NI margin of 3.5 using the confidence interval approach. Assuming a t distribution, the 2-sid ed 95% confidence interval (CI) will be constructed for the mean change (post-baseline - baseline) in ABR. If the upper bound of the CI is less than 3.5, the non-inferiority of BMN 270 versus FVIII prophylaxis in ABR with this margin will be declared.

If non-inferiority is demonstrated, non-inferiority with smaller margins and superiority will be assessed using the same CI. The 2-sided p-value for superiority will be obtained through a one-sample t-test to test the null hypothesis that the change is 0 or greater.

A Wilcoxon signed-rank test and a negative binomial regress model will be used as sensitivity analyses for testing superiority in ABR.

First-Ranked Secondary Efficacy Endpoint

The first-ranked secondary efficacy endpoint is change from baseline in FVIII activity, as measured by chromogenic substrate assay, at Week 104 post-BMN 270 infusion.

The primary analysis of the first-ranked secondary efficacy endpoint will be based on the mITT population. The baseline FVIII activity value will be imputed as 1 IU/dL since there was no washout of severe hemophilia A subjects' usual FVIII prophylaxis (in order to avoid increasing the risk of bleeding) prior to BMN 270 infusion. FVIII activity values post BMN 270 infusion will be excluded from analysis if obtained within 72 hours (or 3 calendar days if time is not available) following an exogenous FVIII infusion. To reduce variation caused by random fluctuation, FVIII activity will be analyzed as the median of observed values in the

visit windows as defined in Section 20.1 of the 2-year analysis SAP. Missing data will be imputed as follows:

- Dropout missing
 - o For subjects who discontinue from the study early, missing FVIII activity values post-discontinuation will be imputed to be 0 IU/dL through the data cutoff date for the analysis.
- Intermittent missing
 - o For subjects who continue on study, missing FVIII activity values (eg, due to a missed study visit) will be imputed to be the smaller of the last prior non-missing value and the next non-missing value. In rare cases where the next value is unavailable for a subject who did not drop out, the missing value will be imputed through linear extrapolation using the last two prior non-missing values.

A one-sample t-test will be used to test the null hypothesis that the change in FVIII activity from baseline to Week 104 (Week 104 - baseline) is 0 or less (ie, superiority when the null hypothesis is rejected). Summary of FVIII activity over time, including at Week 104, will be provided for descriptive purposes.

A complete case analysis (without missing data imputation), a mixed model for repeated measures (MMRM) approach, a last observation carried forward (LOCF) approach, and imputing missing data to be 0 IU/dL will be used as sensitivity analyses for testing superiority.

Additional details about the sensitivity analyses as well as the missing data imputation will be provided in the 2-year analysis SAP.

Second-Ranked Secondary Efficacy Endpoint

The second-ranked secondary efficacy endpoint is change from baseline in annualized utilization (IU/kg) of exogenous FVIII replacement therapy.

The primary analysis of the second-ranked secondary efficacy endpoint will be based on the 270-902 Rollover Subjects. The baseline FVIII utilization under FVIII prophylaxis will be based on the data collected in 270-902. The FVIII utilization post-BMN 270 infusion will be based the data collected in the efficacy evaluation period defined as Week 5 to each subject's last visit up to the analysis data cutoff date.

A one-sample t-test will be used to test the null hypothesis that the change from baseline in annualized FVIII utilization (post-baseline - baseline) is 0 or greater (ie, superiority when the null hypothesis is rejected). Change from baseline in annualized FVIII infusion rate (AFR)

Page **145**

number of exogenous FVIII infusions/year) will be analyzed similarly for descriptive purposes.

Safety Endpoints

Analysis of safety endpoints will be descriptive.

The incidence of AEs will be summarized by system organ class, preferred term, relationship to study drug, seriousness, and severity. A by-subject listing will be provided for subjects who experience a SAE, including death, or experience an AE associated with early withdrawal from the study. Clinical laboratory test values, vital signs, vector shedding and immune response parameters will be summarized descriptively by visit.

Additional details on the primary analysis of the key efficacy and safety endpoints, as well as the planned supportive, sensitivity, and subgroup analyses and analyses for the other endpoints will be provided in the 2-year analysis SAP.

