25.3.5 Interim Analyses and Control of Type I Error Rate

Prior to this 2-year analysis, two protocol-specified interim analyses and a 1-year analysis were planned, of which one interim analysis and the 1-year analysis were performed.

Two interim analyses were planned after approximately 16 and 20 treated HIV-negative subjects have completed the Week 26 visit (or have discontinued study prior to Week 26), respectively. The concept of the interim analyses was to facilitate initiation of regulatory review of the ongoing study in the event that robust improvements (essentially normalization) in FVIII activity in a sufficient proportion of the subjects are observed. The primary efficacy endpoint was subject's FVIII response status, where a subject was considered as a responder if the median FVIII activity per chromogenic assay during Weeks 23-26 post-BMN 270 infusion is \geq 40 IU/dL. The alpha levels of 0.0002 and 0.001 were allocated to the first and second interim analysis, respectively. The second interim analysis would only occur if the result from the first interim analysis was not positive (ie, if the pre-specified statistical significance was not achieved). A 1-year analysis was planned after all subjects have been followed for 52 weeks post-BMN 270 infusion (or have discontinued study prior to Week 52). The efficacy endpoints included change from baseline (prior to BMN 270 infusion while receiving FVIII prophylaxis) in ABR for treated bleeds, change from baseline (assuming no treatment for severe hemophilia A) in FVIII activity per chromogenic assay at Weeks 49-52, and change from baseline (prior to BMN 270 infusion while receiving FVIII prophylaxis) in annualized FVIII utilization. These endpoints were tested sequentially using a hierarchical testing procedure at the alpha level determined by the fallback procedure (Wiens 2005) to control the family-wise type I error rate at 0.05. Results

from this analysis were intended to support regulatory submissions to EMA and other health authorities outside of FDA.

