The first interim analysis was performed in May 2019 (data cut-off date: 30 April 2019) after 16 directly enrolled, HIV-negative subjects have completed the Week 26 visit. Based on the analysis results (p=0.001) and the totality of the data, the secondary interim analysis was deemed unnecessary (the test would be statistically significant at the pre-specified significance level of 0.001) and therefore never implemented. The 1-year analysis was performed in January 2021 (data cut-off date: 16 November 2020) after all subjects had been followed for 52 weeks post-BMN 270 infusion. Results from all pre-specified tests were statistically significant (p < 0.0001) at the alpha level of 0.0498 that was determined by the fallback procedure.

- If the first interim p-value ≤0.0002, the first interim result is declared significant and the 1-year analysis is carried out at the 0.05 level.
- If the first interim p-value >0.0002, the first interim result is not declared significant and the second interim analysis is carried out at 0.001 level. If the second interim p-value <=0.001, the second interim result is declared significant and the 1-year analysis is carried out at the 0.0498 level.
- If the second interim p-value >0.001, the interim results are not declared significant and the 1-year analysis is carried out at the 0.0488 level.

As specified in the 1-year analysis SAP (version 3.0, dated 17 December 2020), in the event that a 2-year final analysis is necessary, the testing procedure used in the 1-year analysis will be extended to the 2-year final analysis. That is, when all pre-specified tests are statistically significant at the 1-year analysis, the corresponding efficacy endpoints at 2 years will be tested in the same sequence under the same significance level.

Based on the fallback procedure and positive results from the 1-year analysis, the 2-year final analysis will be performed at the significance level of 0.0498 and the efficacy endpoints will be tested in the following hierarchical testing sequence:

1. For non-inferiority of BMN 270 versus FVIII prophylaxis in ABR with a NI margin of 3.5

Null hypothesis: post-baseline ABR – baseline ABR ≥ 3.5

2. For superiority of BMN 270 versus no treatment for severe hemophilia A in FVIII activity

Null hypothesis: FVIII activity at Week 104 – baseline FVIII activity ≤ 0

3. For superiority of BMN 270 versus FVIII prophylaxis in FVIII utilization

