Null hypothesis: post-baseline FVIII utilization – baseline FVIII utilization ≥ 0

4. For superiority of BMN 270 versus FVIII prophylaxis in ABR

Null hypothesis: post-baseline ABR – **baseline ABR** ≥ **0**

After the 2-year final analysis, safety and efficacy will then continue to be assessed long-term in all subjects for a total of approximately 5 years.

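### The ABR non-inferiority rule in Section 25.3.6 uses a 95% interval, but Section 25.3.5 sets the 2-year level at 0.0498, which calls for a 95.02% interval

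*Protocol*

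**What the plan says.** Both statements are in Appendix 2 of the Protocol (the United States 2-year analysis).

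- **Level.** Section 25.3.5 uses the fallback procedure "to control the family-wise type I error rate at 0.05" at the 1-year analysis and carries the same procedure forward to 2 years. On the interim analyses it says: "The alpha levels of 0.0002 and 0.001 were allocated to the first and second interim analysis, respectively". The full level is available on one branch only: "If the first interim p-value ≤0.0002, the first interim result is declared significant and the 1-year analysis is carried out at the 0.05 level". The first interim result is then reported: "Based on the analysis results (p=0.001) and the totality of the data, the secondary interim analysis was deemed unnecessary". The section concludes that "the 2-year final analysis will be performed at the significance level of 0.0498". ABR non-inferiority with margin 3.5 is the first test in the 2-year sequence.
- **Decision rule.** Section 25.3.6 states that a 2-sided "95% confidence interval (CI) will be constructed for the mean change (post-baseline - baseline) in ABR", and non-inferiority is declared if the upper bound lies below 3.5. It continues: "If non-inferiority is demonstrated, non-inferiority with smaller margins and superiority will be assessed using the same CI". The next sentence obtains a 2-sided superiority p-value from a one-sample t-test.
- **Order.** Section 25.3.5 tests FVIII activity second and FVIII utilization third, and lists last "4. For superiority of BMN 270 versus FVIII prophylaxis in ABR".

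**The concern.** A 2-sided 95% interval compared with a margin is a test at 2-sided level 0.05. Section 25.3.5 grants 0.05 only if the first interim p-value was at most 0.0002, and it was 0.001. The decision threshold written for the primary endpoint is therefore not the one that the error-control section allows, and nothing in Appendix 2 adjusts the interval.

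The second, smaller point is one of wording. Section 25.3.6 read alone mentions only non-inferiority as the condition for assessing superiority in ABR, whereas Section 25.3.5 puts two other tests in between. What is at stake is that the document should give one unambiguous threshold, and one unambiguous gate, for the main regulatory claims.

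**Working it through.** **Inputs.** Family-wise level 0.05; interim allocations 0.0002 and 0.001; first interim p=0.001; 2-year level 0.0498; margin 3.5 (all Section 25.3.5). Decision interval 95%, 2-sided (Section 25.3.6). Planning values for the ABR change: mean -2.5, SD 8, n=110 (Section 14.8).

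**Step 1: reproduce the plan's level.**
- Weight left for the last stage: 0.05 - 0.0002 - 0.001 = 0.0488.
- First interim: 0.001 > 0.0002, so it is not significant and its 0.0002 is not passed on.
- Second interim counted as significant, as Section 25.3.5 does: 0.001 + 0.0488 = 0.0498. This is the stated figure exactly.

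**Step 2: level of the written rule.**
- 1 - 0.95 = 0.05, that is 0.025 at the upper bound.
- Level granted: 0.0498, that is 0.0249 at the upper bound.
- Excess: 0.0002 two-sided, 0.0001 at the bound.
- Nominal 2-sided sum with the unrecovered first allocation: 0.0002 + 0.05 = 0.0502, against 0.05. With the granted level it is 0.0002 + 0.0498 = 0.05. The 0.001 is not added again, because it is already inside the 0.0498.

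**Step 3: matching interval.** 100(1 - 0.0498)% = 95.02%.

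**Step 4: size of the difference.** Half-width = t(109) × 8/√110, with 8/√110 = 0.7628.

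| Level | Interval | t(109) | Half-width | Largest mean change that passes 3.5 |
|---|---|---|---|---|
| 0.05 | 95% | 1.9820 | 1.5118 | 3.5 - 1.5118 = 1.9882 |
| 0.0498 | 95.02% | 1.9837 | 1.5131 | 3.5 - 1.5131 = 1.9869 |

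The bound moves by 1.5131 - 1.5118 = 0.0013 bleeds per year. From the noncentral t distribution, superiority power is 90.12% at 0.05 and 90.09% at 0.0498, and non-inferiority power exceeds 99.9% at both. The 90.12% agrees with the protocol's figure of about 90%.

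**Step 5: order of tests.** Section 25.3.5 runs non-inferiority in ABR, FVIII activity, FVIII utilization, superiority in ABR. Section 25.3.6 is arranged by endpoint and so treats both ABR tests together, with non-inferiority as the stated condition for superiority. Step 4 of the sequence also requires step 1, so the two texts can both be true. Section 25.3.6 simply omits the other two conditions.

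**The case against.** The strongest case against the point is that it makes no difference. The bound shifts by about 0.0013 against a margin of 3.5, power is unchanged for practical purposes, and the 1-year tests are all reported at p < 0.0001. The hypothesis is also one-directional, so the chance of a false non-inferiority claim at the margin is 0.025 rather than 0.0249. The 0.0502 is a nominal 2-sided sum, an upper bound and not a realised error rate. All of this stands, and it limits the weight of the point. It does not remove the mismatch between two current statements about the same test.

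A second objection is that Section 25.3.1 gives the SAP precedence over the protocol on statistical methods. That rule settles differences between the two documents. It does not reconcile two sections of the protocol with each other. It does mean that nothing can be said here about how the analysis will be carried out; only the protocol wording is open to criticism.

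On superiority, a reader might infer that Section 25.3.6 permits a claim as soon as non-inferiority is shown, so that ABR superiority and FVIII activity would run as parallel branches, each at the full level. The documents do not support this. Section 25.3.5 gives an explicit sequence with ABR superiority fourth, which excludes parallel branches. The condition in Section 25.3.6 reads naturally as necessary rather than sufficient, and that section speaks of declaring a result only for non-inferiority. The superiority p-value that it specifies can also be compared directly with 0.0498.

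**Conclusion.** The point holds as an inconsistency in a stated decision threshold: 0.05 in Section 25.3.6 against 0.0498 in Section 25.3.5, for the primary 2-year test. Its numerical size is about 0.0013 bleeds per year on the confidence bound, taking n=110 and SD 8 from the planning section. A conclusion could change only if the bound fell within roughly that distance of 3.5 (or of 0, for superiority), so practically no plausible result is affected. It is worth correcting because the error-control plan is stated to four decimals and the primary rule should follow it.

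The order of the superiority test is a matter of clarity, not a contradiction.

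The calculation takes 0.0498 as Section 25.3.5 sets it. That figure counts the second interim analysis, which was never carried out, as significant. If it were counted as not significant, the section's own rule would give 0.0488, a 95.12% interval and a half-width of 1.5199. Tying the interval to the level, rather than to a fixed percentage, covers either case.

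**What to change.** In Section 25.3.6, replace the fixed 95% by the 2-sided 100(1 - alpha)% interval at the level set in Section 25.3.5, which is 95.02% at 0.0498. Use it for the ABR decisions on non-inferiority, smaller margins and superiority. A 95% interval can still be reported as an estimate.

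Add one cross-reference: ABR superiority is claimed only as step 4 of Section 25.3.5, after steps 1 to 3 are significant; otherwise its p-value is descriptive.

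The cost is two sentences in Appendix 2, with the SAP kept in line, made before the 2-year analysis. The decision interval widens by about 0.0013 bleeds per year on each side. Sample size, conduct and data collection are not touched.

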14.3 Secondary Efficacy Endpoints

The primary analyses for the secondary endpoints will be performed on the 110 subjects in the mITT population who will be followed up for approximately 6 months in the non-interventional study 270-902 prior to their enrollment in 270-301. The baseline values will be derived from the prospectively collected data in 270-902.

For the first-ranked secondary efficacy endpoint (ie, the change in the annualized utilization (IU/kg) of exogenous FVIII replacement therapy in the efficacy evaluation period ("Week 5 to Last Visit") from baseline), a one-sample t-test will be performed to test the null hypothesis that the change is 0 or greater against the alternative hypothesis that the change is less than 0. The missing value of the change will be imputed as 0.

For the second-ranked secondary efficacy endpoint at Week 52 (ie, the change in ABR in the efficacy evaluation period ("Week 5 to Last Visit") from baseline), a one-sample t-test will be performed to test for non-inferiority of BMN 270 against FVIII prophylaxis (ie, the baseline ABR calculated using subjects' data collected as part of 270-902) using a non-inferiority margin of 3.5, ie, to test the null hypothesis that the change is 3.5 or greater against the alternative hypothesis that the change is less than 3.5. If non-inferiority is

demonstrated, the test for superiority of BMN 270 against FVIII prophylaxis will be performed. The missing value of the change will be imputed using the median value of the changes of all observed cases.

A sensitivity analysis is planned to analyze ABR using a generalized linear mixed model assuming negative binomial as the underlying distribution. The model will include period (pre-to post-BMN 270 infusion) as the only factor. The actual number of bleeding episodes will be used as the dependent variable with the time period adjustment (annualization) being implemented as the offset.

To assess the impact of missing data, analyses using observed case are planned as sensitivity analyses for the secondary endpoints. Multiple imputation methods may also be performed.

The primary and secondary efficacy hypotheses will be tested hierarchically according to the order described above. Multiple comparison procedures will be described in greater detail in the SAP.

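### Appendix 2, section 25.3.6 does not follow the testing scheme of 25.3.5: it uses a 95% interval where the level is 0.0498, and names non-inferiority as the only condition for ABR superiority

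*Protocol*

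**What the plan says.** Section 25.3.5 fixes the level: "the 2-year final analysis will be performed at the significance level of 0.0498". It then numbers four tests:

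1. ABR non-inferiority with a margin of 3.5
2. superiority in FVIII activity at Week 104
3. superiority in FVIII utilization
4. "For superiority of BMN 270 versus FVIII prophylaxis in ABR"

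Section 25.3.6 describes the ABR analysis separately. A 2-sided 95% "confidence interval (CI) will be constructed for the mean change (post-baseline - baseline) in ABR", and non-inferiority is declared if its upper bound lies below 3.5. The next paragraph begins: "If non-inferiority is demonstrated, non-inferiority with smaller margins and superiority will be assessed using the same CI". It goes on to specify a 2-sided superiority p-value from a one-sample t-test.

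Section 25.3.6 mentions neither 0.0498 nor steps 2 and 3, and it does not refer back to 25.3.5. The smaller margins do not appear in the 25.3.5 sequence.

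**The concern.** A fixed sequence protects the error rate because each test opens only after every earlier one has been rejected. For the primary endpoint of the US analysis the protocol gives two different gates to the superiority claim. In 25.3.5 it is steps 1 to 3; in 25.3.6 it is step 1 alone. If FVIII activity or utilization failed, one section would forbid an ABR superiority claim and the other would allow it.

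Moving from non-inferiority to superiority on one interval normally costs no alpha. That holds when nothing stands between the two tests. Section 14.3 has a similar step, and it is harmless there because ABR is the last endpoint in that section's order. In Appendix 2 two other endpoints stand in between, so the same move opens a second branch.

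The interval level is a smaller matter of the same kind: 95% corresponds to 0.05, not to 0.0498.

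**Working it through.** **The plan's level.** Section 25.3.5 states: "The alpha levels of 0.0002 and 0.001 were allocated to the first and second interim analysis, respectively", within a scheme meant "to control the family-wise type I error rate at 0.05". The fallback arithmetic is:

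- left for the last analysis: 0.05 − 0.0002 − 0.001 = 0.0488
- if only the second interim counts as rejected: 0.0488 + 0.001 = 0.0498
- if both count as rejected: 0.05

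All three match the levels in 25.3.5. The 0.0498 assigned to the 2-year analysis is taken as given here.

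**The interval.** A 2-sided interval at 0.0498 has confidence 1 − 0.0498 = 95.02%. Section 14.8 gives n = 110 and a mean (SD) change of −2.5 (8). The half-width is t(109) × 8/√110.

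| | 95% | 95.02% |
|---|---|---|
| t(109) | 1.9820 | 1.9837 |
| Half-width, bleeds/year | 1.5118 | 1.5131 |
| Power for superiority | 0.9012 | 0.9009 |

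The 95% column reproduces the roughly 90% superiority power stated in 14.8. Using the matching level adds 0.0013 bleeds/year, about 0.09%, to the half-width.

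**The gate.**

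| Result of steps 1 to 3 | ABR superiority under 25.3.5 | Under 25.3.6, read literally |
|---|---|---|
| All rejected | tested | tested |
| Step 1 rejected, step 2 or 3 not | not tested | tested |
| Step 1 not rejected | not tested | not tested |

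The sections differ in the middle row.

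**Effect on the error rate.** Suppose the true ABR change and the true FVIII activity change are both 0. Non-inferiority at 3.5 is then true and is shown with probability about 0.995 (n = 110, SD 8), so step 1 restrains almost nothing. The null hypotheses are directional, so a false claim of benefit uses one tail of each 2-sided test.

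- Strict order: superiority cannot be reached without first falsely rejecting FVIII activity. The error is at most 0.0498/2 = 0.0249.
- Superiority opened by non-inferiority alone, at the 95% level: at most 0.0249 + 0.05/2 = 0.0499. With independent statistics it is 1 − (1 − 0.0249)(1 − 0.025) = 0.0493.

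A simulation of 400,000 runs with normal statistics gave 0.0493 with no correlation, and 0.0452 and 0.0488 at correlations of −0.5 and +0.5. Under the strict order it gave 0.0237 to 0.0249.

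**The case against.** The strongest reply is that 25.3.5 governs order and error control, while 25.3.6 only describes the statistic for each endpoint. It states no cross-endpoint gate for FVIII activity or utilization either. On that reading non-inferiority is a necessary condition for superiority, not a sufficient one, and nothing says that steps 2 and 3 may be skipped. This reading is possible, and it limits the seriousness of the point. It does not remove it: for the other two endpoints 25.3.6 states no condition, whereas for ABR superiority it states one and omits the rest.

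The protocol also lets the SAP prevail where the two differ on statistical methods (14.10 and 25.3.1). That settles differences between SAP and protocol, not a conflict between two protocol sections. The scenario is also remote: 25.3.5 reports p < 0.0001 for all pre-specified 1-year tests. That stands, and it bears on severity.

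A reader might also infer three stronger points that the documents do not support:

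- That the error rate rises to 2 × 0.0498 = 0.0996. This counts both tails of directional hypotheses; the relevant bound is 0.0499.
- That the interval should be 95.12%, from 0.0488. Section 25.3.5 assigns 0.0498 to the 2-year analysis, so the matching interval is 95.02%.
- That the 2-year order itself is undefined. Section 25.3.5 says that "the corresponding efficacy endpoints at 2 years will be tested in the same sequence under the same significance level", and 14.3 ranks ABR after FVIII activity and utilization, adding: "The primary and secondary efficacy hypotheses will be tested hierarchically according to the order described above". But 25.3.5 itself lists the 1-year endpoints with ABR first, rests the rule on a 1-year SAP that is not shown, and gives the explicit 2-year steps together with the condition that all 1-year tests succeeded.

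**Conclusion.** Section 25.3.6 is wrong as written; the severity in practice is minor. The substantive part is the gate. Read literally, it lets ABR superiority be claimed after step 2 or 3 fails, which raises the one-sided family-wise error from about 0.025 to at most about 0.05. That figure assumes that the ABR and FVIII activity changes are both truly 0; the simulated values also assume normal statistics with SD 8 and n = 110. The interval mismatch is real but numerically negligible.

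It would be wrong to infer that the primary non-inferiority claim is in doubt. ABR non-inferiority at 3.5 is tested first under both sections, and only the later superiority claim and the smaller margins are affected.

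**What to change.** In 25.3.6:

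- Build the ABR interval as a 2-sided 95.02% interval (1 − 0.0498), or tie it in words to whatever alpha finally applies.
- State that ABR superiority is confirmatory only after steps 1 to 3 of 25.3.5 have been rejected.
- Label the smaller-margin assessments descriptive.

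The 2-year SAP should carry the same wording. The cost is a few sentences, about 0.0003 in superiority power (0.9012 to 0.9009), and no change to sample size, conduct or data collection. The change should be in place before the 2-year data cutoff, given in 25.3.2 as approximately 15 November 2021.
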